The treatment patterns and outcomes of two sub-groups are of great interests. The first subgroup is the elderly. Given the highly concentrated nature of U-500R, physicians have hesitation in using U-500R with their elderly patients. Even though elderly accounted for about 50% of the U-500R initiators in an ongoing study (full RWE cohort), no studies have explicitly examined the safety and efficacy of U-500R in elderly. Information on the effectiveness and safety of U-500R among elderly will be valuable to HCPs and patients. The other subgroup of interests are those whose U-500R daily dose is in the range of 201-300 units/day. While most physicians are confident with the use of U-500R when patients insulin needs exceed 300 units/day, this is not the case in the range of 201-300 units for some physicians. Currently only less than 20% of patients on 201-300 units/day insulins use U-500R (internal data-on-file). Therefore, it is important to understand the compliance, effectiveness, and safety among those who were on 201-300 units/day of U-500R insulin. Additionally, the U-500R Kwikpen was launched in 2016. Therefore, a 9-months pre- and post-index period will be applied in the VHA to ensure adequate sample size due to the recent launch of the Kwikpen. Since VHA does not have reliable cost data, Truven database is used to understand out-of-pocket costs and will be assessed using a 12-months pre- and post-index period to ensure deductibles are properly captured for all patients.

The aim of this study is to provide a comprehensive understanding of U-500R in high-dose cohort (defined by having an average TDD of >180 units per day, with no additional insulin used concomitantly with U-500R or pump use), including compliance, effectiveness, safety, and out-of-pocket costs, rather than just one particular aspect of U-500R. Ideally, an integrated database with both claims and EMR data will be needed for such a study. Unfortunately, while VHA database is an integrated claims and EMR database, it lacks reliable costs data. As a result, out-of-pocket costs aspect will be examined separately using IBM MarketScan data.

[2019-8636] Observational Study Protocol**4. Objectives****4.1 Research Objectives****Research Objective 1: Treatment Patterns**

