5.1 Summary of Research Design

This will be a retrospective cohort study using the Veterans Health Administration (VHA) database and the Truven[®] MarketScan[®] claims databases.

Study outcomes will be assessed using multiple datasets to ensure availability of target outcomes (e.g., out-of-pocket costs are available in the Truven dataset but not the VHA dataset; HbA1c data are available in the VHA dataset but not the Truven dataset). Furthermore, the patient population in the VHA primarily consists of veterans across the country (non-commercial database), whereas Truven is an employment-based health insurance (commercial database). Therefore, conducting the analysis separately in each of these databases will give a more comprehensive and complete picture of the real-world treatment patterns and outcomes in this patient population.

- ❖ To meet the analytical requirement of multiple research objectives, the following criteria will be used:
 - The first prescription claim date for U-500R syringe or U-500R Kwikpen administration will be considered U-500R initiation and designated as Index Event (syringe: Index Event **a**; Kwikpen: Index Event **b**; Any U-500R use: Index Event **c**).
 - The study period will range from 01APR2013–31MAR2018 for VHA; and 01JUL2013–30JUN2018 for Truven MarketScan claims.
 - The identification period will be 01JAN2014–30JUN2017 for VHA; and 01JUL2014–30JUN2017 for Truven MarketScan claims; the pre- and post-index periods will be 9 months for the VHA and 12 months for the Truven databases, respectively (Figures 1-3).

[2019-8636] Observational Study Protocol

Figure 1 Study Design for U-500R Syringe Initiation (Index Event a)

[figure not shown]
[figure not shown]
[figure not shown]

Figure 2 Study Design for U-500R Kwikpen Initiation (Index Event b)

[2019-8636] Observational Study Protocol

Figure 3 Study Design for Any U-500R Initiation (Index Event c)

Note: The figures above depict a schematic representation of the study design using the study periods for the VHA database. For analysis conducted in the Truven database, a 12-month pre-index period and a 12-month post-index period will be used instead of 9 months to ensure deductibles are properly captured for all patients.

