5.3. Study Population

5.3.1 Selection Criteria

U-500R Syringe Initiators [Index Event a]

Inclusion Criteria

Patient will be included if they:

- had ≥ 1 prescription claim for U-500R vial during the identification period (VHA: 01JAN2014–30JUN2017; Truven: 01JUL2014–30JUN2017), with the first prescription claim for U-500R vial designated as index Event a (U-500R syringe initiation), and the date designated as the index date;
- had ≥ 2 claims with an ICD-9/10-CM code (Appendix 1) for T2DM in any position (primary/secondary) at any time prior to the index date;
- were aged ≥ 18 years on the index date;
- had continuous health plan enrollment with medical and pharmacy benefits for ≥ 9 months pre- and post-index event;
- had ≥ 1 prescription claim for any insulin other than U-500R in the pre-index period;
- had ≥ 1 HbA1c measurement within 90 days pre-index or 30 days post-index event;
- had ≥ 1 HbA1c measurement after the 30-day post-index period at any time in the 9-month post-index period;

[2019-8636] Observational Study Protocol

- had claims indicating TDD >180 in the post-index period;
- had claims indicating TDD >180 in the pre-index period; and

Exclusion Criteria

Patient will be excluded if they:

- had both T1DM and T2DM, had no oral anti-diabetic drug (OADs; Appendix 1) other than metformin, and the ratio between the number of T1DM and T2DM claims >0.5 at any time in the study period (VHA: 01APR2013–31MAR2018; Truven: 01JUL2013–30JUN2018);
- had previous use of U-500R in the 9-month pre-index period;
- had ≥ 1 claim with an ICD-9/10-CM code (Appendix 1) for secondary diabetes, gestational diabetes, diabetes complicating pregnancy, childbirth, puerperium, or non-clinical diabetes at any time during the 9-month pre-index period;
- had claims indicating pump use (Appendix 2) in the 9-month post-index (follow-up) period;
- had claims indicating TDD above 2000 units/day at any time in the pre-index or post-index periods; or
- had claims indicating insulin use other than U-500R in the post-index period.

U-500R Kwikpen Initiators [Index Event **b**]Inclusion Criteria

Patient will be included if they:

- had ≥ 1 prescription claim for U-500R Kwikpen administration during the identification period (VHA: 01JAN2014–30JUN2017; Truven: 01JUL2014–30JUN2017), with the first prescription claim for U-500R Kwikpen administration designated as Index Event **b**, and the date designated as the index date;

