- had ≥ 2 claim with an ICD-9/10-CM code (Appendix 1) for T2DM in any position (primary/secondary) at any time prior to the index date;
- were aged ≥ 18 years on the index date;
- had continuous health plan enrollment with medical and pharmacy benefits for ≥ 9 months pre- and post-index event;
- had ≥ 1 prescription claim for any insulin other than U-500R (Table 1) in the pre-index period;
- had ≥ 1 HbA1c measurement within 90 days pre-index or 30 days post-index event;
- had ≥ 1 HbA1c measurement after the 30-day post-index period at any time in the follow-up period;
- had claims indicating TDD >180 in the post-index period;

[2019-8636] Observational Study Protocol

- had claims indicating TDD >180 in the pre-index period; and

Exclusion Criteria

Patient will be excluded if they:

- had both T1DM and T2DM, had no OADs (Appendix 1) other than metformin, with the ratio between the number of T1DM and T2DM claims >0.5 at any time in the study period (VHA: 01APR2013–31MAR2018; Truven: 01JUL2013–30JUN2018);
- had previous use of U-500R in the 9-month pre-index period;
- had ≥ 1 claim with a ICD-9/10-CM code (Appendix 1) for secondary diabetes, gestational diabetes, diabetes complicating pregnancy, childbirth, puerperium, or non-clinical diabetes at any time during the pre-index period;
- had evidence of pump use (Appendix 2) in the post-index period;
- had claims indicating TDD above 2000 units/day at any time in the pre-index or post-index periods; or
- had claims indicating insulin use other than U-500R in the post-index period.

Sample selection criteria for any U-500R Initiators [Index Event c]Inclusion Criteria

Patient will be included if they:

- had ≥ 1 prescription claim for U-500R syringe or Kwikpen administration during the identification period (VHA: 01JAN2014–30JUN2017; Truven: 01JUL2014–30JUN2017), with the first prescription claim for U-500R syringe or Kwikpen administration designated as Index Event c, and the date designated as the index date;
- had ≥ 2 claim with an ICD-9/10-CM code (Appendix 1) for T2DM in any position (primary/secondary) at any time prior to the index date;
- were aged ≥ 18 years on the index date;
- had continuous health plan enrollment with medical and pharmacy benefits for ≥ 9 months pre- and post-index event;
- had ≥ 1 prescription claim for any insulin other than U-500R (Table 1) in the pre-index period ;
- had ≥ 1 HbA1c measurement within 90 days pre-index or 30 days post-index event;

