- had ≥ 1 HbA1c measurement after the 30-day post-index period at any time in the follow-up period;
- had claims indicating TDD >180 in the post-index period; and
- had claims indicating TDD >180 in the pre-index period

[2019-8636] Observational Study ProtocolExclusion Criteria

Patient will be excluded if they:

- had both T1DM and T2DM, had no OADs (Appendix 1) other than metformin, with the ratio between the number of T1DM and T2DM claims >0.5 at any time in the study period (VHA: 01APR2013–31MAR2018; Truven: 01JUL2013–30JUN2018);
- had previous use of U-500R in the 9-month pre-index period;
- had ≥ 1 claim with a ICD-9/10-CM code (Appendix 1) for secondary diabetes, gestational diabetes, diabetes complicating pregnancy, childbirth, or puerperium, or non-clinical diabetes at any time during the pre-index period;
- had evidence of pump use (Appendix 2) in the follow-up period;
- had claims indicating TDD above 2000 units/day at any time in the pre-index or post-index periods; or
- had claims indicating insulin use other than U-500R in the post-index period.

Note:

- All high-dose U-500R patients will be defined by having an average TDD of >180 units per day, with no additional insulin used concomitantly or no U-500R pump use.
- Since the Truven claims database does not include lab data, the ≥ 1 HbA1c criterion will be removed from the selection criteria while using this database.
- For analysis conducted using the Truven claims database, the pre-index period and the post-index period will be 12 months instead of 9 months.
- The corresponding ICD-9/10 codes for all the diagnoses and the NDC codes for the insulin treatments are provided in Appendix 1.

Subgroup analysis:

- Elderly (≥ 65 years) patients among each of the high-dose U-500R Kwikpen, high-dose U-500R syringe, and any high-dose U-500R initiator cohorts will be flagged, and a subgroup analysis will be performed comparing the treatment patterns and outcomes (HbA1c and hypoglycemia) before and after U-500R initiation.
- Patients with a TDD of 201-300 units in the post-index period among each of the high-dose U-500R Kwikpen, high-dose U-500R syringe, and any high-dose U-500R initiator cohorts will be flagged, and a subgroup analysis will be performed comparing the treatment patterns and outcomes (HbA1c and hypoglycemia) before and after U-500R initiation.

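### Kwikpen cohort: U-500R use before the 9-month (Truven 12-month) pre-index window is not screened, so lapsed vial users are eligible as U-500R initiators

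*Protocol*

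**What the plan says.** Section 5.1 of the protocol defines the exposure start: "The first prescription claim date for U-500R syringe or U-500R Kwikpen administration will be considered U-500R initiation and designated as Index Event". There are three index events: syringe (a), Kwikpen (b) and any U-500R (c).

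Section 5.3.1 then sets the index dates and the prior-use screen:

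- Cohort b: "with the first prescription claim for U-500R Kwikpen administration designated as Index Event b, and the date designated as the index date".
- Cohort c: "with the first prescription claim for U-500R syringe or Kwikpen administration designated as Index Event c, and the date designated as the index date".
- Each cohort excludes patients who "had previous use of U-500R in the 9-month pre-index period". A note changes the length for one database: "For analysis conducted using the Truven claims database, the pre-index period and the post-index period will be 12 months instead of 9 months".
- The type 2 diabetes diagnosis, by contrast, is searched without a time limit: "for T2DM in any position (primary/secondary) at any time prior to the index date".

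The Background states that "the U-500R Kwikpen was launched in 2016" and that U-500R itself was first approved in 1994. Sections 5.1 and 5.4 start the data on 01APR2013 (VHA) and 01JUL2013 (Truven) and close the identification period on 30JUN2017. No criterion, flag, covariate or sensitivity analysis in the protocol deals with U-500R use before the pre-index period.

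**The concern.** The objectives contrast treatment patterns, HbA1c and hypoglycemia before and after high-dose initiation of U-500R by each route. That reading needs a before period that is free of the drug's earlier influence. In cohort b the clock starts at the first Kwikpen claim, not the first U-500R claim, and the vial was on the market throughout. A patient could use the vial in 2014, stop, take other insulin, and fill a Kwikpen in 2016. If the other criteria are met, this patient is admitted, and the before period then comes after an earlier course of the study drug and after whatever led to stopping it. The response to the Kwikpen may also differ from that of a patient new to U-500R.

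This bears on both primary objectives and on Secondary Objective 2a in the Kwikpen cohort. It also means that cohorts b and c can disagree about when, or whether, the same person initiated U-500R.

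**Working it through.** **1. Are the windows consistent?** Yes. VHA: 01APR2013 plus 9 months is 01JAN2014, the start of identification, and 30JUN2017 plus 9 months is 31MAR2018, the end of the study period. Truven closes in the same way with 12 months. The screen is exactly the minimum look-back.

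**2. How much calendar time before a Kwikpen index is not screened?** Assume that the earliest possible index is 01JAN2016, since the protocol gives only the launch year. The latest is 30JUN2017. Unscreened span = (index date − data start) − screen length.

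| Database | Data start to index | Screened | Unscreened | Unscreened share |
|---|---|---|---|---|
| VHA | 33 to 51 months | 9 | 24 to 42 | 73% to 82% |
| Truven | 30 to 48 months | 12 | 18 to 36 | 60% to 75% |

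These are calendar spans of the dataset. Enrolment is required only for the pre-index window, so they are upper limits on what can be seen for a given patient.

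**3. Why cohort b more than cohort c?** In c, a vial claim inside the identification period itself sets the index date. Earlier use that c can miss is thus confined to data before identification begins: at most 9 months in VHA (01APR2013 to 31DEC2013) and 12 in Truven. In b, a vial claim never sets the index date, so the whole span in step 2 is open.

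**4. Do b and c agree on the same person?** Two VHA cases, assuming that all other criteria of the cohort in question are met:

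- First vial claim in 2014, stopped, first Kwikpen claim in 2016 after more than 9 months without U-500R. The c index is in 2014 and the b index in 2016.
- Vial use in late 2013, refill in January 2014, stopped that year, Kwikpen in 2016. Cohort c excludes the patient for prior use in the 9 months before the January 2014 claim. Cohort b admits the patient.

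**5. What size could the effect be?** The protocol gives no count of lapsed users. Table 3 goes from 741 to 647 Kwikpen patients in a last step (94 patients) that pools several criteria, so prior use cannot be isolated. For illustration only:

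Shift in mean HbA1c change = r × d, where r is the share of lapsed users and d is the difference between their mean change and that of the other patients. Both are assumed. For d, take half to all of the approximately 0.7-point drop that the Background quotes from an earlier Kwikpen study.

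| r | Patients of 647 | d = 0.35 | d = 0.7 |
|---|---|---|---|
| 5% | 32 | 0.018 | 0.035 |
| 10% | 65 | 0.035 | 0.07 |
| 20% | 129 | 0.07 | 0.14 |

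With r = 2% (13 patients) and d = 0.2 the shift is 0.004 points. The sign depends on whether returning users respond less or more than new users, which is unknown.

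**The case against.** A fixed washout is a common and defensible choice in claims research. It treats every index date alike, whereas a search of all data gives a January 2014 vial index about 9 months of look-back and a June 2017 Kwikpen index up to 51. It cannot establish never-use either, since U-500R dates from 1994. The group at issue is narrow: off U-500R for at least 9 months, other insulin at TDD >180, then U-500R alone at TDD >180 without a pump, with HbA1c at both points in VHA. Such patients are true first-time Kwikpen users, and they meet Table 2's definition of the pre-index exposure. All of this stands, and it limits the weight of the point. The unlimited search for the diabetes diagnosis is also only a weak parallel, because a chronic diagnosis and a drug exposure need not share a look-back.

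A reader might go further than the protocol allows in four ways:

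- **That most available patient history is ignored.** The spans in the working are not guaranteed enrolment. Section 5.2 says that 73% of recent MarketScan patients have even 12 months of continuous enrolment.
- **That the 5,162 syringe users in Table 3 are a pool of former users.** The count includes continuing users, late starters, and direct switchers to the Kwikpen, whom the screen already removes.
- **That the pre-index HbA1c captures U-500R withdrawal.** It is measured no earlier than 90 days before index, so about 6 months or more after the last U-500R claim (9 − 3).
- **That the Kwikpen results are not effects of initiation at all.** The text supports only possible contamination, to an unknown degree.

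What remains is that the protocol calls the index claim U-500R initiation, leaves a gap that is widest for the Kwikpen, and provides nothing to detect it. Eligibility is settled in the protocol, so this is not a detail that an analysis plan would normally decide.

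**Conclusion.** The point holds as one of eligibility and labelling. Lapsed vial users can enter the Kwikpen cohort as U-500R initiators, their before period then follows earlier exposure, and cohorts b and c can classify the same person differently. That follows from the selection criteria and the dates alone, given a Kwikpen launch no earlier than 01JAN2016.

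Whether such patients are numerous, and whether they move any estimate, cannot be derived from the protocol. The 0.02-0.14 point range rests on assumed shares of 5-20% and an assumed difference of 0.35-0.7 points. The 0.7 comes from a study in which 62% of patients had an average TDD of 200 units or less before initiation, a different population from this high-dose cohort. The range applies to VHA only, because Truven has no HbA1c. The change is worth making because it is cheap and answers the question directly, not because a large bias has been shown.

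**What to change.** Keep the 9-month (Truven 12-month) criterion as the minimum look-back. Add to cohort b, and for consistency to a and c, an exclusion for any U-500R claim, vial or Kwikpen, in the study data before the index date (VHA from 01APR2013, Truven from 01JUL2013). Alternatively, keep these patients and analyse them as a separate returning-user group. In either case, report how many patients are affected in each cohort and show the results with and without them. If the number is trivial, the count alone settles the matter.

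The cost is a short change to the selection criteria and one query on data already inside the study period. The downsides are a slightly smaller Kwikpen cohort and a look-back that varies with index date and enrolment. Reporting both results makes these visible. Use before the data start stays undetectable and should be stated as a limitation.

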5.3.2 Subject Groups

After applying the selection criteria, our analysis will focus on the following cohorts.

Index Event a

[2019-8636] Observational Study Protocol

- high-dose U-500R Syringe Initiators Cohort: Patients who initiated U-500R syringe administration (Index Event **a**) on their index date.

Index Event b

- High-dose U-500R Kwikpen Initiators Cohort: Patients who initiated U-500R Kwikpen administration (Index Event **b**) on their index date.

Index Event c

- Any high-dose U-500R Initiators Cohort: Patients who initiated U-500R (vial or Kwikpen; Index Event **c**) on their index date. The first prescription claim for vial or Kwikpen will be defined as the index date.

Note: In each of the abovementioned cohorts, subgroups of elderly patients (≥ 65 years), patients with TDD 201-300 units/day and (optional) those who had TDD >300 units/day will be identified for the subgroup analysis.

5.4 Time Periods

The study period will range from 01APR2013–31MAR2018 for VHA, and 01JUL2013–30JUN2018 for Truven MarketScan claims. The identification period will be 01JAN2014–30JUN2017 for VHA, and 01JUL2014–30JUN2017 for Truven MarketScan claims. The pre-index and post-index periods will be 9 months for the VHA and 12 months for the Truven MarketScan database, respectively (Figures 1-3).

5.5 Variables/Measures

Table 2 presents the study variables and operational definitions.

Table 2 Variables and Definitions

Variable	Source	Definition
Exposure		
Insulin use	Truven: Outpatient pharmacy claims table VHA: Pharmacy file	Index Event a : any insulin use other than U-500R in the pre-index and high-dose U-500R syringe use in the post-index period Index Event b : any insulin use other than U-500R in the pre-index and high-dose U-500R Kwikpen use in the post-index period Index Event c : any insulin use other than U-500R in the pre-index and high-dose U-500R Kwikpen/syringe use in the post-index period
Patient Characteristics*		

[2019-8636] Observational Study Protocol

Variable	Source	Definition
Age	Truven: Inpatient service table, outpatient service table, outpatient pharmacy claims table VHA: Enrollment file	Age will be retained in the dataset as a continuous variable for groups aged 18-25, 26-35, 36-45, 46-55, 56-64, and ≥ 65 years.
Sex	Truven: Inpatient service table, outpatient service table, outpatient pharmacy claims table VHA: Enrollment file	A flag will be created for male and female patients.
Race (only VHA)	VHA: Enrollment file	A flag will be created for white, black, and other race patients.
US Region (only Truven)	Truven: Inpatient service table, outpatient service table, outpatient pharmacy claims table	A flag will be created for patients residing in the Northeast, Northcentral, South, and West US regions.
Medicare eligibility (only Truven)	From Truven	A flag will be created for patients who are enrolled in Truven Medicare.
Body mass index (BMI)	VHA: Vital Status file	BMI on the index date will be calculated and reported as a continuous variable.
Quan-Charlson comorbidity index (CCI) score ²⁶	Truven: Inpatient service table, outpatient service table VHA: Inpatient and outpatient files	Quan-CCI score will be constructed using enhanced ICD-9/10-CM codes for 17 different comorbid conditions.
Individual Comorbidities ²⁷	Truven: Inpatient service table, outpatient service table VHA: Inpatient and outpatient files	A flag will be created using ICD-9/10-CM codes (Appendix 1) for patients diagnosed in the pre-index period with any of the following individual comorbidities: retinopathy, nephropathy, neuropathy, coronary artery disease, peripheral vascular disease, congestive heart failure, hypertension, depression, obesity, or malignant tumor.
Health Economics Outcomes Research (HEOR) Outcomes		

[2019-8636] Observational Study Protocol

Variable	Source	Definition
Observed TDD in claims	Truven: Outpatient pharmacy claims table VHA: Pharmacy file	
The observed insulin TDD will be calculated as the total number of insulin units/total unique days of supply as recorded in claims and will be calculated both in the pre-and post-index periods among the high-dose U-500R Kwikpen initiators, high-dose U-500R syringe initiators, and any high-dose U-500R initiators. TDD will be reported as both a continuous and categorical variable.
 
For high-dose U-500R syringe initiators (Index Event a):
 
Total insulin units correspond to all the insulin units in pre-index and post-index periods, respectively.
 
For high-dose U-500R Kwikpen initiators (Index Event b):
 
Total insulin units correspond to all the insulin units in pre-index and post-index periods, respectively.
 
For any high-dose U-500R initiators (Index Event c):
 
Total insulin units correspond to all the insulin units in pre-index and post-index periods, respectively.
 
Note:
 
For the unique days supply in patients with evidence of a basal-bolus regimen, or basal/bolus-pre-mixed or basal/bolus-U-500R, the overlap days will be adjusted for the concomitant use of basal and bolus insulin products, but will not be adjusted within basal and within bolus insulins.

Change in observed TDD		The change in observed TDD will be defined as the difference between the pre- and post-index observed TDD.

[2019-8636] Observational Study Protocol

Variable	Source	Definition
Observed average daily dose (ADD) in claims	Truven: Outpatient pharmacy claims table VHA: Pharmacy file	
The observed insulin ADD will be calculated both in the pre-and post-index periods among the high-dose U-500R Kwikpen initiators, high-dose U-500R syringe initiators, and any high-dose U-500R initiators. ADD will be reported as both a continuous and categorical variable.
 
Pre-index ADD: the total number of insulin units/the total number of days in the pre-index period.
 
Post-index ADD: the total number of insulin units/ the total number of days in the post-index period
 
Note: Total insulin units calculation in based on the similar approach as described in TDD.

Adherence	Truven: Outpatient pharmacy claims table VHA: Pharmacy file	
Adherence to insulin will be assessed using the proportion of days covered (PDC), and reported in categories of 0-20%, 20-40%, 40-60%, 60-80%, and 80%-100%. PDC will be calculated both in the pre-and post-index periods among the U-500R Kwikpen initiators, U-500R syringe initiators, and any U-500R initiators.
 
For high-dose U-500R syringe initiators (Index Event a): PDC before U-500R initiation will be calculated as the number of days covered by the prescription claims of insulin (any insulin)/total days in the pre-index period. PDC after U-500R initiation will be calculated as the number of days covered by the prescription claims of insulin /total days in the post-index period.
 
For high-dose U-500R Kwikpen initiators (Index Event b):

[2019-8636] Observational Study Protocol

Variable	Source	Definition
		
PDC before U-500R initiation will be calculated as the number of days covered by the prescription claims of insulin (any insulin)/total days in the pre-index period.
 
PDC after U-500R initiation will be calculated as the number of days covered by the prescription claims of insulin /total days in the post-index period.
 
For any high-dose U-500R initiators (Index Event c):
 
PDC before U-500R initiation will be calculated as the number of days covered by the prescription claims of insulin (any insulin)/total days in the pre-index period.
 
PDC after U-500R initiation will be calculated as the number of days covered by the prescription claims of insulin /total days in the post-index period.
 
Note: For the calculation of PDC in patients with evidence of a basal-bolus regimen, basal/bolus-premixed, or basal/bolus-U-500R, the overlap days will be adjusted for the concomitant use of basal and bolus insulins, but will not be adjusted within basal and within bolus insulins.

Abandonment/fill rates	Truven: Outpatient pharmacy claims table VHA: Pharmacy file	The average number of insulin prescription fills will be calculated in the follow-up period among all the study cohorts.
Claim gaps	Truven: Outpatient pharmacy claims table VHA: Pharmacy file	The average gap between prescription fills of insulins will be calculated in the pre- and post-index periods among all the study cohorts.
Concomitant medications ^{28,29,30}	Truven: Outpatient pharmacy claims table VHA: Pharmacy file	A flag will be created for patients prescribed the following antihyperglycemic agents (AHA):

[2019-8636] Observational Study Protocol

Variable	Source	Definition
		thiazolidinediones, sulfonylureas, biguanides, meglitinides, alpha-glucosidase inhibitors, DPP-4 inhibitors, SGLT-2 inhibitors, bile acid sequestrants, fixed-dose combinations, GLP-1 receptor agonists, and amylin agonists (Appendix 1).
HbA1c ³¹	VHA: Lab file	The HbA1c value in the pre-index and post-index period for each index event will be reported. Pre-index HbA1c will be the HbA1c measurement -90/+30 days of the index date. For patients with multiple HbA1c measurements within this period, the measurement taken closest to the index event date will be reported as the pre-index HbA1c value. The post-index HbA1c value will be the farthest HbA1c measurement taken in the time period after the 30 day-post index event date.
Change in HbA1c		The change in HbA1c will be defined as the difference in the pre-index and post-index HbA1c values.
Hypoglycemic events	Truven: Inpatient service table, outpatient service table VHA: Inpatient and outpatient files, Lab file and Pharmacy file	Hypoglycemia events in the pre- and post-index periods will be evaluated using the ICD-9 codes from the Ginde algorithm (Appendix 1), ³² the presence of a cutoff of blood glucose ≤ 70 mg/dL, or any evidence of intramuscular glucagon administration (Appendix 1). Hypoglycemia events that occurred on or after the index date will be considered the follow-up hypoglycemia event; and hypoglycemia event occurred on or prior to - 1 day of the index date will be considered as the pre-index hypoglycemia event. The number of hypoglycaemia events per patient per year (PPPY) will be reported in both the pre-and post-index periods.

[2019-8636] Observational Study Protocol

Variable	Source	Definition
Out-of-pocket costs	Truven: Inpatient service table, outpatient service table, outpatient pharmacy claims table	
Out-of-pocket pharmacy costs will be computed among T2DM patients before and after high-dose U-500R syringe initiation, high-dose U-500R Kwikpen initiation, and any high-dose U-500R initiation.
 
Out-of-pocket pharmacy costs will be further classified into:
 
 • Diabetes-related out-of-pocket pharmacy costs (i.e., the costs associated with any insulins and AHAs [sulfonylureas, TZD, biguanides, meglitinides, alpha-glucosidase inhibitors, DPP-4 inhibitors, SGLT-2, bile acid sequestrant, fixed-dose combination, GLP-1, pramlintide) • Insulin-related out-of-pocket pharmacy costs • All-cause out-of-pocket pharmacy costs (i.e., all the pharmacy costs in the 12 months period) 
Costs will be adjusted to 2018 US dollars using the annual medical care and drug costs components of the Consumer Price Index (CPI) to reflect inflation.

Note: Treatment pattern in the Truven database will be conducted using the 12-month pre- and post-index period.

[2019-8636] Observational Study Protocol

6. Sample Size and Statistical Methods**6.1 Determination of Sample Size**

The preliminary sample sizes for the VHA databases from 2013–2018 are shown below. This study will use the most recent 5 years of data available.

Table 3. Preliminary Sample Size

Database	Counts
VHA (01APRIL2013–31MARCH2018)	
Kwikpen:	
Evidence of U-500R Kwikpen during the identification period	2,596
Evidence of T2DM	2,536
≥1 HbA1c in the pre-index and post-index periods	741
After applying other inclusion/exclusion criteria and excluding patients with pump use along with U-500R Kwikpen	647
Syringe Use:	
Evidence of U-500R syringe use during the identification period	5,162
Evidence of T2DM	4,956
≥1 HbA1c in the pre-index and post-index periods	1,930
After applying other inclusion/exclusion criteria and excluding patients with pump use along with U-500R syringe	1,766

